9.10. Health-related quality of life questionnaires

All patients will be asked to fill in a health-related quality of life (EQ-5D) questionnaire, time to return to normal function (SF36) and a VAS scoresheet for chest pain and breathlessness.

EQ-5D-5L

The EQ-5D is a 5-domain questionnaire which gives an overall assessment of an individual's quality of life at a particular time point. There are five questions, and it is envisaged this should take between 1-2 minutes to complete. These assessments will take place in person at baseline, 14 days +/- 3, 28 days +/-3 days and remotely in 90 days +/- 3 days.

VAS score

RAPTOR – f study uses a VAS score instrument to record patients' reported chest pain and shortness of breath. The patient will be asked to mark on a line scale their assessment of their symptoms at that time. This should take around 30 - 45 seconds per scale. These will be collected at baseline, day 28 + -3 days in person and day 90 + -3 days (remotely)

SF36

This survey assesses eight health concepts: physical functioning, bodily pain, role limitations due to physical health problems, role limitations due to personal or emotional problems, general mental health, social functioning, energy/fatigue, and general health perceptions. It takes 6 to 8 minutes to fill out, this assessment will take place at day 28 + _ 3 days and day 90+_ 3 days.

9.11. Embedded Qualitative Interviews

An important aspect of a feasibility study is the participant's experience of the study processes, interventions and follow-up is an important aspect of the RATOR f feasibility study. A selection of patients who were eligible for the RAPTOR f study (both those who accepted randomisation and those who did not) will be invited to semi-structured interviews. A selection of healthcare professionals (Respiratory/pleural or general physicians) who were responsible for the clinical care of participants in the RAPTOR f study will be invited towards the end of the recruitment period.

Declining entry into the RAPTOR f study will not preclude a patient from being invited to interview, as the views of patients who declined randomisation will be particularly valuable.

Patient interviews

Patients who accepted randomisation will be given the interview specific participants information sheet (PIS) at 14 days post-discharge (at the time of the first clinic visit for all participants and the second clinic visit for the low risk group). The interviews will take place 4 to 6 weeks after study recruitment to allow time for recovery of the participant.

For those who did not accept randomisation, the members of the clinical team will explore their willingness to take part in a qualitative interview while they are inpatient or when attend their clinic follow up. If they are willing, they will be given the participant information sheet r the qualitative study and the team will seek their permission to pass on their contact details to the study fellow [name] via secured email system. The research team will then contact them to arrange an interview, which will be conducted at a time convenient to the patient participant at 4 to 6 weeks after hospital discharge, in order to ensure recovery.

Participants will be invited to online interviews via Microsoft Teams or a telephone call if unable to access online audio team call. The interview will be conducted at a time convenient for the patient. Interviewees will be asked to provide remote verbal informed consent at time of to the interview., Professional translation services will be provided for non-English speakers.

The interview topic guides (for patients and for healthcare professionals) have been developed in collaboration with a pleural infection PPI group and submitted for ethical approval. The interviews will explore the following topics: acceptability of study design (e.g. recruitment, consenting, randomisation) and treatment arms; factors influencing study participation; the impact of pleural infection and study participation on the quality of life and carers; and important health outcomes.

A sample of up to 12patients who were eligible for enrolment in the RAPTOR f study will be invited to participate in interviews to ensure that that there is sufficient information for the topics covered in the interview guide and no new issues are emerging.

Healthcare Professionals Interview

Up to six healthcare professionals who will be significantly involved with the care of study participants, will be invited to participate in an interview near the end of the recruitment period. An information sheet will be provided to each of the Healthcare Professionals and a minimum of 24 hours to consider their participation. The process of obtaining consent for the interviews will mirror that used for the patient interviews, with written informed consent required prior to the commencement of the interview. This consent will include permission for the physician's comments to be recorded and for anonymised quotes to be included in the final report and any peer-reviewed literature arising from the project.

The interview topic guide will focus on the following areas:

- The experience of using the risk stratification tools, RAPID score to guide management of pleural infection.
- Suggested improvements to the study processes to optimise participant recruitment and retention.
- Understanding physician equipoise e.g. are there any patients with pleural infection that physicians would not be willing to randomise to a study of this type? What are the barriers of recruitment and randomisation
- The study's perceived effect on patient outcomes and healthcare services, as well as recommendations for future research in this field.

As with the patients' interviews, the sample size of up to six physicians has been deemed sufficient to provide enough information for the topics covered in the interview guide and that no new issues are emerging.

All interviews

All interviews will last up to 60 minutes. This will be conducted by [name], or one of the members of the study team via online platforms e.g. Microsoft Teams, audio function or Telephone call for those who don't have access to the internet. It will be audio-recorded, professionally transcribed by transcription services, the transcripts will remain confidential during the transfer and storage process, the company will destroy the audio-files and any copies they held of the transcript. The transcription company will be approved by, and contracted to, the university. Transcripts will be securely returned to study team, checked and any remaining identifying information removed, then to uploaded to data management software. The data will be thematically analysed under the supervision of [name].

9.12. Sample Handling

Samples for routine clinical care will be conducted as per local hospital practice and NHS standard care. Research samples from all participants consenting to provide samples (blood and pleural fluid) will be collected and transported to the coordinating centre for analysis as per study-specific processing procedures.

9.12.1. Bloods

All blood tests (e.g. CRP, FBC) performed during the RAPTOR f feasibility study are part of the NHS standard care for patients with pleural and systemic infection. These tests will include full blood count, , C-reactive protein, and liver and renal function tests which are advisable to be taken on alternate days if feasible for the first 7 days and then once or twice per week as deemed appropriate by the treating physician if the participant stays over a week. These samples will be processed at each recruiting centre via normal laboratory processes. The results will be recorded on the case reports form.

In addition, all participants will be asked for specific consent for collection of repeated samples of blood (10 millilitres, about 2 teaspoonfuls) on days 1 (randomisation day), 3 and 5 post -randomisation from all centres (Optional) if these are convenient to collect (e.g. if the patient has been discharged home, they will not be collected or day o sample only) and to avoid any discomfort for the patients all research samples will be collected at the same time of usual care samples. We will assess the levels of the biomarkers, including suPAR (Soluble Urokinase Plasminogen Activator Receptor) and PAI-1 (Plasminogen-Activator Inhibitor-1), cytokines (Interleukins (IL) 1 and 2, and NE (Neutrophils elastase) assessments at baseline from all participants at baseline and we will repeat the measurement on day 3 and 5 if applicable and participant willing to donate the samples.

9.12.2. Pleural fluid

As part of the NHS standard care for diagnosis and management of pleural infection, a diagnostic pleural aspiration is performed, which will occur before/or at the time of enrollment in RAPTOR f study. This includes pleural fluid total protein (TP), lactate dehydrogenase (LDH), glucose, pH, cytology and standard microbiology (culture and microscopy in white top containers or blood culture bottles), the results will be recorded in the study database system. If any of the above standard pleural fluid investigations were not

requested, they could be performed on this pleural fluid collected during chest tube insertion as per standard care or add on request to the laboratory after therapeutic aspiration.

In addition, all participants from all centres **(optional)** will be asked for specific consent for the collection of repeated samples of pleural fluid (100 ml) on days 1 (randomisaiton day, 3 and 5, post — randomisation), if these are convenient to collect (e.g. if the patient has been discharged home, they will not be collected or day 1sample only), and to avoid any discomfort for the patients all research samples will be collected at the same time of usual care samples. These samples will be used for analysis of pleural fluid biomarkers, including suPAR (Soluble Urokinase Plasminogen Activator Receptor) and PAI-1 (Plasminogen-Activator Inhibitor-1), cytokines (Interleukins (IL) 1 and 2, and NE (Neutrophils elastase) assessments. They will also be consented **(optional)** to store and use the leftover samples after completing the analysis for the ethically approved future research. The participant will be assured that consent for the samples storage and use is not required for participation and enrolment into the clinical study.

10. Early Discontinuation/Withdrawal of Participants

During the course of the study, a participant may choose to withdraw early from the study treatment at any time. This may happen for several reasons, including but not limited to:

- The occurrence of what the participant perceives as an intolerable AE.
- Inability to comply with study procedures
- Participant decision

Participants may choose to stop treatment and/or study assessments but may remain on study follow-up, participants may also withdraw their consent, meaning that they wish to withdraw from the study completely. They have the right to withdraw from the study at any time without having to give a reason and this will not affect their future care.

Withdrawal of a participant from the study should be under the guidance of the principal investigator (in liaison with the CI). Withdrawal details will be recorded on the relevant CRF.

Participants are only withdrawn if they specifically request no further data collection. In the event of participants not wishing to attend visits, or to discontinue treatment, they are not considered withdrawn, but this will be recorded as a file note/protocol deviation. Should a participant decide to withdraw, all efforts will be made to complete and report the observations as thoroughly as possible. For participants moving from the area, every effort should be made for the participant to be followed up at another centre, or for follow-up via GP.

Finally, the Investigator may discontinue a participant from the study arms at any time if the Investigator considers it necessary for any reason including:

- I. Ineligibility (either arising during the study or retrospectively having been overlooked at screening)
- II. Significant protocol deviation
- III. Significant non-compliance with the study requirements

If the participant is withdrawn due to an adverse event directly related to the study, the Investigator will

Clinical Research Protocol Template version 15.0

CONFIDENTIAL

Date and version No: 03/06/2025_ V2.0 arrange for follow-up visits or telephone calls until the adverse event has resolved or stabilised.

11. Definition of End of Study

The end of the study is the point at which all the data have been entered, follow-up completed, queries resolved, data lock complete and research samples analysed or at the discretion of the Study Steering Committee (SSC).

12. SAFETY REPORTING

All treatment modalities that will be used in the RAPTOR -f feasibility study (interventional and non-interventional treatments), including chest drain insertion, therapeutic aspiration, IET, antibiotics, and surgery have all been clinically approved and are part of the NHS routine standard usual care; therefore, only SAEs that are found to be directly related the a study procedure and not expected will be reported.

12.1. Definition of Serious Adverse Events

A serious adverse event is any untoward medical occurrence that:

- · results in death
- is life-threatening
- requires inpatient hospitalisation or prolongation of existing hospitalisation
- results in persistent or significant disability/incapacity
- consists of a congenital anomaly or birth defect.

Other 'important medical events' may also be considered a serious adverse event when, based upon appropriate medical judgement, the event may jeopardise the participant and may require medical or surgical intervention to prevent one of the outcomes listed above.

NOTE: The term "life-threatening" in the definition of "serious" refers to an event in which the participant was at risk of death at the time of the event; it does not refer to an event which hypothetically might have caused death if it were more severe.

12.2. Reporting Procedures for Serious Adverse Events

A serious adverse event (SAE) occurring to a participant should be reported to the REC that gave a favourable opinion of the study where in the opinion of the Chief Investigator the event was 'related' (resulted from administration of any of the research procedures) and 'unexpected' in relation to those procedures. Reports of related and unexpected SAEs should be submitted within 15 working days of the Chief Investigator becoming aware of the event, using the HRA report of serious adverse event form (see HRA website).

13. STATISTICS AND ANALYSIS

The plan for the statistical analysis of the study is outlined below. There will not be a separate SAP document in use for the trial, as the analysis is relatively simple.

13.1. Description of the Statistical Methods

13.1.1. Analysis of the RAPTOR f feasibility study:

Feasibility parameters will be measured and reported, and include:

- Recruitment proportion (number of randomised patients divided by number of eligible patients)
- Randomisation acceptance rate (proportion of patients who are willing to be randomised over those eligible)
- Retention (number of participants who complete intended treatment, number of participants who complete intended follow up)

These will be reported and used to assess whether or not a definitive trial is feasible. Descriptive statistics will be used to describe the demographic characteristics between the two groups. For categorical variables, numbers (and proportions) will be reported for each treatment group and overall. For continuous variables, means and standard deviations (or medians in the interquartile range) will be reported for each treatment group and overall. As this feasibility study is not powered to draw definitive conclusions, comparisons between the two arms for clinical outcomes will be reported using descriptive statistics only. No statistical tests will be carried out. These will be based on multivariable linear (for continuous outcomes) or logistic (for binary outcomes) regression with adjustment for stratification factors and important prognostic factors and will be reported as adjusted differences in means (for continuous outcomes) or proportions (for binary outcomes). Treatment comparisons will be reported for the intention-to-treat population (all randomised participants will be analysed according to their allocated treatment group irrespective of which treatment they actually receive) as treatment effects together with 95% confidence intervals for the two main comparisons: (1) Standard care vs overall RAPID driven treatment (2) Low RAPID driven treatment arm vs moderate to high RAPID driven treatment arm. Compliance to the interventions will be reported.

To establish the feasibility of collecting accurate long-term outcomes in randomised participants, we will present the completeness of the outcomes across the duration of the trial. The outcome measures collected in this study will be used to inform the sample size for the future definitive large-scale phase III RCT if it is feasible to be undertaken.

Adverse events and serious adverse events will be reported by each arm in the intervention group on the safety population only (all patients who received the allocated treatment).

It is anticipated that STATA (StataCorp LP) or other appropriate validated statistical software will be used for analysis.

13.1.2. Analysis of the embedded qualitative:

Interviews will be digitally audio-recorded, transcribed verbatim, and de-identified before being uploaded to data management software. The interview data will be analysed using Thematic Analysis. Audio-recordings will be listened to, and transcripts read and re-read for familiarisation, then opencoded to develop an initial code list. Codes will then be grouped into categories, and data explored to identify connections and to develop a descriptive account of the dataset as a whole. The analysis will

focus on the acceptability of study processes to patients, individual and group equipoise, and the patient experience of pleural infection and treatment.

For the RAPTOR-f study and embedded qualitative interviews, we will use robust progression criteria (see Table 1) to assess the feasibility of progression to a definitive phase III trial; green indicates all criteria are met, and if met, a larger study will be declared feasible. If one or more criteria are amber, this will result in mitigations including:

- o Review of qualitative data to identify barriers and potential mitigations
- o Discussion of recruitment to date and barriers with the study management group
- o Consideration of widening the recruited population and increasing centres

Table 1: Illustrate stop and go criteria for study progression, this will be applied for all centres, if any criteria are red, this will prompt major changes to the study or qualitative study design.

Criteria	Green	Amber	Red
Recruitment proportion (number eligible versus number randomised)	>50%	30% - 50%	< 30
Average monthly recruitment* (pts/centre/month)	≥1.0	0.5 – 0.9	< 0.5
Adherence to the allocated intervention group	≥90%	75% - 90%	< 75%
The proportion of key date completion (e.g Visual Analogue Score)	≥98%	75% - 97%	< 75%
Proportion completing study protocol (accounting for 10% expected attrition)	≥90%	75% - 90%	< 75%
Individual site recruitment (at 10 months)	≥10	5 – 9	< 5
Proportion completing clinicians' interview	>50 %	30% - 50%	< 30%
Proportion completing patients' interview	>50%	30% - 50%	< 30%

^{*} Once all centres have been greenlighted

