3. SYNOPSIS

Study Title	RAPTOR – RAPID driven Treatment of Pleural Infection (feasibility study)			
Internal ref. no. / short title	RAPTOR -f			
Study registration	25/WA/0161	25/WA/0161		
Sponsor	University of Oxford Research Governance, Ethics and Assurance Team [name] [contact] [contact]			
Funder		Health and Care Research, Research on number NIHR207229	for Patient Benefit	
Study Design	Feasibility study			
Study Participants	 Adults with confirmed pleural infection requiring admission to hospital with: 1. A clinical presentation compatible with pleural infection or infective illness. 2. A pleural collection on radiology (CXR, ultrasound or CT) with a chest drain in situ or planned 3. Pleural fluid features diagnostic of infection which is either: A. purulent or B. gram positive or C. culture positive (pleural fluid or biopsy) or D. acidic with a pH<7.2 or E. low pleural fluid glucose <4.4 mmol/L or 72mg/dL(non-diabetic) or LDH ≥ 900 iu/L OR F. (non-fluid criteria) – CT findings suggestive of pleural infection (pleural enhancement) or pleural fluid septations on thoracic ultrasound 			
Sample Size	30 participants randomised (15 in each arm) from 3 to 4 centres		centres	
Planned Study Period	01/06/2025 - 01/03/2027			
Planned Recruitment period	10 months		_	
	Objectives	Outcome Measures	Timepoint(s)	
Primary	To assess the feasibility of recruitment, data collection and acceptability of the	 30 patients randomised 1:1 between RAPID driven treatment versus standard treatment. Recruitment and 	1. At recruitment completion	

			1
	participants and of Healthcare professionals of randomisation.	retention rate, the proportion of participants screened who consented to be randomised and who consented to be interviewed. Data completeness/availability and participant completion.	
		2. To conduct semistructured interviews with a proportion of the randomised participants and healthcare professionals	2. 4 to 6 weeks post hospital discharge
		3. The primary outcome will be defined as successful if ≥50% of the eligible patients are willing to be randomised and ≥ 50% of the healthcare provisional and participant agreed to take part into the interviews	3. At recruitment completion

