9.5. Randomisation

Following consent and baseline assessment, randomisation will occur via a secure web-based system Sealed Envelope by a member of the RAPTOR f research team at the site. Randomisation will occur once the pleural infection has been confirmed by the documented inclusion criteria. This may occur after the therapeutic pleural aspiration or once a chest drain has been inserted or with a high suspicion of pleural infection. Participants will be randomly allocated to one of two arms of the study in a 1:1 ratio to either standard care or RAPID-driven treatment, see study flow diagram (Chart 1). Randomisation will be randomly generated by the Sealed Envelope software to reduce selection bias.

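### Section 13.1.1 is wrong as written: arm comparisons are to be descriptive only, yet also regression effects adjusted for stratification factors that the protocol does not have and prognostic factors it does not name

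*Protocol*

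**What the plan says.** Section 13.1.1 first states that "comparisons between the two arms for clinical outcomes will be reported using descriptive statistics only". It then continues: "No statistical tests will be carried out. These will be based on multivariable linear (for continuous outcomes) or logistic (for binary outcomes) regression". The models are to be "regression with adjustment for stratification factors and important prognostic factors", giving adjusted differences in means or proportions. These are to be presented, for the intention-to-treat population, "as treatment effects together with 95% confidence intervals for the two main comparisons". The two comparisons are standard care against the whole RAPID-driven arm, and low against moderate-to-high RAPID score within the RAPID-driven arm.

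On allocation, Section 9.5 says only this: "Participants will be randomly allocated to one of two arms of the study in a 1:1 ratio", and "Randomisation will be randomly generated by the Sealed Envelope software to reduce selection bias". It gives no stratum or minimisation factor. The size is "30 participants randomised (15 in each arm) from 3 to 4 centres" (Synopsis). Section 13 adds: "There will not be a separate SAP document in use for the trial, as the analysis is relatively simple". Section 13.6 gives the significance level as not applicable.

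**The concern.** Two different analyses are fixed in adjoining sentences, and the second cannot be carried out as described. One of its covariate sets does not exist in the randomisation section and the other is not named. With no separate SAP, nothing else settles the matter, and Section 13.8 measures deviations against this same text. An analyst could report bare summaries or a multivariable model and claim compliance either way.

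The choice matters most for binary outcomes such as death and surgery. With few events spread over several covariates, a logistic model can fail to give a finite estimate. The second comparison raises a further problem. It sets two risk strata of one arm side by side, and these differ by prognosis and by assigned pathway at once. Nothing in it is randomised, yet the text calls the result a treatment effect.

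**Working it through.** **1. Text against text.**

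| Element | Section 13.1.1 | Elsewhere in the protocol |
|---|---|---|
| Type of analysis | Descriptive only, then adjusted regression effects with 95% intervals | 13.6: significance level not applicable |
| Stratification factors | To be adjusted for | 9.5: 1:1 allocation, no factor given |
| Prognostic factors | To be adjusted for, none named | RAPID score calculated in the intervention arm only (7.1; Section 9 table, footnote 5) and not routinely under standard care (9.7) |
| Where detail could sit | – | 13: no separate SAP |

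**2. The plan's own figure.** The only formula-based sample size is that of the future trial (13.2): SD 10, difference 4 days, 5% significance, 90% power. Per arm, 2 × (1.960 + 1.282)² × 10² / 4² = 131.4, rounded up to 132, so 264 in total. This reproduces. The feasibility figure of 30 has no power calculation to reproduce.

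**3. Events available.** Section 5 gives 20% mortality: 30 × 0.20 = 6 deaths (central 80% range 3 to 9), about 3 per arm. Section 13.2 expects half of the RAPID arm to be low risk, so comparison 2 has about 7 versus 8 patients and about 15 × 0.20 = 3 deaths.

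**4. Unadjusted loss of the estimate (exact).** A logistic estimate is not finite when one group has no deaths.
- Comparison 1: 1 − (1 − 0.8¹⁵)² = 6.9%.
- Comparison 2, 20% in both strata: 1 − (1 − 0.8⁷)(1 − 0.8⁸) = 34%.
- Comparison 2, 5% low and 35% high: 1 − (1 − 0.95⁷)(1 − 0.65⁸) = 71%.

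**5. Adjusted models (simulation).** There were 1,500 trials per setting, with a linear-programming check for separation. The covariates are assumptions, since the protocol names none. Each cell gives the share of trials at 20% mortality, first with no risk gradient and then with a gradient (5% low, 35% high risk).

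| Comparison 1 model | Any coefficient not finite | Arm coefficient not finite |
|---|---|---|
| Arm only | 7% / 7% | 7% / 7% |
| Arm + risk group | 13% / 46% | 7% / 6% |
| Arm + five RAPID-type items | 35% / 36% | 12% / 13% |
| Arm + 3 sites | not run / 36% | not run / 8% |
| Arm + 3 sites + risk group | not run / 62% | not run / 14% |
| Arm + 4 sites | 64% / 66% | 9% / 8% |
| Arm + 4 sites + risk group | 67% / 81% | 12% / 18% |
| Arm + 4 sites + five RAPID-type items | 76% / 75% | 33% / 36% |

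A different set of two to five prognostic factors gave lower full-model failure without centre terms, about 12–22%, with the arm effect lost in about 7–14%. Adding centre raised full-model failure to about 31–45% (3 centres) and 58–67% (4 centres), with the arm effect lost in about 9–34%.

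In comparison 2 the group coefficient was not finite in 38% / 71% unadjusted (the split between strata was random here) and in 51% / 79% with four sites.

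**6. Sensitivity to the event rate.** At 10% mortality the arm coefficient is lost in 37–75% and the comparison 2 coefficient in 68–91%. At 30% the figures are 1–12% and 33–52%.

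**7. Continuous outcomes.** The linear models can be fitted. For scale, the unadjusted length-of-stay difference has a 95% half-width of 2.048 × 10 × √(2/15) = 7.5 days, against the 4-day difference in 13.2.

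**The case against.** The best defence is that estimates with confidence intervals and no tests are respectable in a feasibility study, and agree with both the no-test sentence and Section 13.6. That is so, and only the restriction to descriptive statistics clashes with them. The clash is still there, and the missing covariates remain.

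Several stronger readings are tempting and not supported:

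- **That most trials of this size would yield no treatment effect.** The high failure rates count any coefficient, and centre terms drive much of them. The protocol never says that centre will be modelled. The arm effect in comparison 1 is lost far less often.
- **That logistic regression cannot deliver the promised differences in proportions.** Standardisation after a logistic fit gives an adjusted risk difference. Separation on a site term alone need not prevent it.
- **That covariates will be picked by whichever model converges.** The protocol leaves room for this but does not say so, and Section 13.8 requires changes to be described and justified.
- **That the go/no-go decision is compromised.** The progression table in Section 13.1.2 uses no between-arm clinical comparison, and Section 13.1.1 itself says the study is not powered for definitive conclusions.

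**Conclusion.** The point holds as a fault in the written rule. The contradiction, the absent stratification factors, the unnamed prognostic factors and the treatment-effect label on a non-randomised contrast can all be read from the text and need no simulation.

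The numerical part is narrower. It concerns logistic models for uncommon binary outcomes and rests on 20% mortality, 15 per arm and assumed covariates. On that basis the arm effect in comparison 1 has no finite estimate in roughly 7–35% of trials. The full model fails in about 12–22% without centre terms for a modest covariate set, and more often when a covariate strongly predicts death or has an uncommon category. With 3 or 4 centres it fails in about 30–75%, and in 81% in the most extreme setting tried. Comparison 2 loses its group coefficient in about 38–79%. This should be corrected, but it does not threaten the feasibility objectives.

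**What to change.** In Section 13.1.1:

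1. Delete the sentence that bases the comparisons on multivariable regression, and fit no adjusted models.
2. Replace the restriction to descriptive statistics. For standard care versus RAPID-driven treatment, report per-arm summaries with the unadjusted difference and its 95% confidence interval (t-interval for means, Newcombe interval for proportions), described as imprecise and not for efficacy inference.
3. Reword the sentence that asks for treatment effects on two main comparisons, so that it covers only the randomised one. Report low versus moderate-to-high RAPID score as summaries within the RAPID-driven arm.

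All three edits are needed: deleting the regression sentence alone leaves the treatment-effect sentence, and intervals would still clash with a descriptive-only rule. Adjusting for RAPID score instead is not a free alternative. The protocol does not provide for the score in the standard care arm, and in comparison 2 the score defines the groups.

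Summaries remain available when a cell is empty: 0 deaths in 15 has an exact 95% interval of 0% to 21.8%, and 3 in 15 has 4.3% to 48.1%. The cost is a reworded paragraph and the loss of covariate-adjusted estimates. Procedures, data collection and progression criteria do not change.
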